The proposed outpatient study will quantify $\alpha 7$ nAChR availability in 18 tobacco cigarette smokers with tobacco use disorder (TUD) using human Positron Emission Tomography (PET) with a $\alpha 7$ nAChR selective radiotracer (^{18}F -ASEM) and explore the potential relationship of $\alpha 7$ nAChR availability to clinically relevant measures of tobacco abstinence (e.g., withdrawal and craving, cognitive impairment). Participants' $\alpha 7$ nAChR availability will be compared to $\alpha 7$ nAChR availability of historical controls (healthy volunteers who were nonsmokers). Study participants and historical controls will be matched by race, sex, and age. Smokers will also complete an 8-day quit attempt during which they can receive an incentive (money), contingent upon target exhaled carbon monoxide (CO) in early abstinence, and target urinary cotinine levels at later abstinence stages. These data are critical towards our understanding of the effects of cigarette smoking on $\alpha 7$ nAChR, a potential pharmacotherapeutic target to promote smoking cessation.

2. Objectives (include all primary and secondary objectives)

The proposed studies will help fill gaps in existing research by determining if $\alpha 7$ nAChR availability in nicotine-dependent cigarette smokers is higher when compared to nonsmoker historical controls using PET imaging and the $\alpha 7$ nAChR selective radiotracer ^{18}F -ASEM. The study will also explore whether distribution volume (V_T), a measure of $\alpha 7$ nAChR availability in tobacco users influences clinically relevant measures of tobacco abstinence (e.g., withdrawal and craving, cognitive impairment), tobacco/nicotine use, and number of days abstinent during an 8-day quit attempt during which smokers can receive escalating payments contingent upon providing objective evidence (breath CO and urinary cotinine) of smoking abstinence.

Primary Objective 1: To examine $\alpha 7$ -nAChR availability in tobacco smokers versus healthy nonsmoker controls.

Hypothesis 1: $\alpha 7$ -nAChR availability (V_T) will be higher in heavy smokers with TUD than nonsmoker historical controls.

Primary Objective 2: To examine the relationship between $\alpha 7$ -nAChR availability and clinically relevant measures of tobacco abstinence.

Hypothesis 2: $\alpha 7$ -nAChR availability (V_T) in smokers will be positively associated with severity of nicotine dependence.

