The primary outcome variable is V_T determined via ^{18}F -ASEM PET scans in 5 VOI (anterior cingulate, hippocampus, frontal cortex, amygdala, and ventral striatum). We completed a power analyses using R, and the package ‘pwr’ version 1.2-1, using pooled baseline data (total $n=21$) and our test-retest data ($n=8$) for ^{18}F -ASEM V_T . Across all regions, TRV averaged 6% ($\pm 0.9\%$, range 5.1% to 8.8% across regions), which is well below the standard accepted reproducibility level of 10%. Assuming between group comparisons (18 Smokers vs. 18 controls), with an α of 0.05 (one tailed test), we examined our power to detect a 20% difference between groups (smokers vs. nonsmokers). Cohen's d for the VOIs, calculated as the average difference in mean V_T for a 20% increase in smokers/pooled standard deviation (SD), ranged from 1.09 (amygdala) to 1.3 (frontal cortex). Our analysis indicated we will have 0.94 to >0.98 power to detect 20% change in our VOIs. If the change is more modest (e.g., 15%), calculated Cohen's d ranged from 0.82 (amygdala) to 0.98 (frontal cortex), and we would still have >0.80 power to detect group differences of 15% in anterior cingulate, hippocampus, frontal cortex, and ventral striatum, but may be slightly underpowered for amygdala (0.77 power) for a 15% group difference.

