Statistical Analysis Plan: First, the baseline characteristics of the participants (age, race, sex, socioeconomic status etc.) will be summarized and compared by group (smokers vs. controls). The primary and secondary outcomes variables as defined in 4.3 Outcome variable, and summarized above, will be our dependent variables. Descriptive statistics will be generated; continuous variables will be reported as means (SD) and categorical variables as frequencies and percentages. The primary outcome variable (V_T), and all secondary outcome variables will undergo data cleansing and CAPA (Corrective/Preventive Measures-based confirmation of accuracy and missing data). We will perform exploratory data analyses (stem-leaf displays, box plots, histograms, and Q-Q plots), and if necessary, appropriate data transformations will be performed. Our intention is to frequency match groups as closely as possible for age, race, and sex, and to match male and female smokers for nicotine dependence severity as appropriate, to reduce these potential confounds. To determine if smokers differ from controls in $\alpha 7$ nAChR availability (hypothesis 1a), we will use a general linear model. V_T (or a transformation, if necessary) will be the dependent variable with group (smokers and controls) as the independent variable. All VOI-based statistical analyses will be done with SPSS (IBM Corp., 2013) or R (Foundation for Statistical Computing, 2011). After the initial VOI-based analyses, we will also use Statistical Parametric Mapping (SPM^(56, 58)) to identify and confirm differences in V_T between groups without restrictions of VOIs. The same models used in VOI-based analyses will be applied to the voxel-based analyses. We plan to use a threshold level of $p = 0.05$, FDR-corrected, and the minimal cluster size at 50 voxels (~ 0.4 ml). To determine if V_T will be associated with clinically relevant measures of tobacco withdrawal during abstinence in smokers, we will construct separate models with V_T of hypothesized VOIs as the dependent variable, and change from baseline to abstinence (day 1) for: craving, withdrawal discomfort, negative affect, and cognitive/memory performance as independent variables. The Holm-Bonferroni method will be applied to correct for multiple comparisons.

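### The power figures for Hypothesis 1 hold only at an unadjusted one-tailed 0.05, and the plan does not say whether Holm-Bonferroni covers its five regional tests

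*Combined protocol and SAP*

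**What the plan says.** - **Section 2, Hypothesis 1** (under Primary Objective 1) is a single global statement: V_T "will be higher in heavy smokers with TUD than nonsmoker historical controls".
- **Section 7, Sample size and Power Analysis** defines the primary outcome as V_T "in 5 VOI (anterior cingulate, hippocampus, frontal cortex, amygdala, and ventral striatum"). It singles out no region and defines no composite. Power is computed for 18 smokers against 18 controls, "with an α of 0.05 (one tailed test"), and multiplicity is not mentioned. The stated results are 0.94 to >0.98 at a 20% difference. At 15%, the plan says "we would still have >0.80 power to detect group differences of 15% in anterior cingulate, hippocampus, frontal cortex, and ventral striatum", with 0.77 for amygdala.
- **Section 7, Statistical Analysis Plan** tests Hypothesis 1 with a general linear model of V_T on group. It gives no number of models, alpha, sidedness or success rule, and asks whether the groups differ. For the voxel maps it sets an FDR-corrected threshold and adds: "The same models used in VOI-based analyses will be applied to the voxel-based analyses". It then describes separate models relating V_T to craving, withdrawal, affect and cognition, followed by: "The Holm-Bonferroni method will be applied to correct for multiple comparisons". The family of tests is not defined.
- The same paragraph refers the reader to a section 4.3 on outcome variables, which this document does not contain.

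**The concern.** The plan does not say what result would support Hypothesis 1: a difference in any region, in all regions, or in a summary of them. The error rate and the power both depend on that answer.

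Five separate regional tests are the natural reading, because power is given region by region and the same models are reused voxel by voxel. On that reading there are two possibilities:

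- **Holm covers Hypothesis 1.** The stated figures are then not the power of the planned tests, and a null region at a true 15% difference would be judged against a figure that is too high.
- **Holm does not cover Hypothesis 1.** One nominally significant region out of five could then be reported as confirming the primary hypothesis, with a familywise error well above 0.05.

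**Working it through.** **Inputs from Section 7, Sample size and Power Analysis.** n = 18 per group; one-tailed 0.05; d = 1.09 (amygdala) to 1.30 (frontal cortex) at 20%; d = 0.82 to 0.98 at 15%. No d is given for anterior cingulate, hippocampus or ventral striatum.

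**Assumptions.** All five regions are affected, and they are equally correlated with r = 0.5 to 0.9. The documents give no correlation.

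**1. Reproduce the stated figures.** Power of a two-sample t-test comes from the noncentral t with df = 2 × 18 − 2 = 34 and noncentrality d × √(18/2) = 3d.

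| d | Noncentrality | One-sided 0.05 | Stated | One-sided 0.01 |
|---|---|---|---|---|
| 0.82 | 2.46 | 0.778 | 0.77 | 0.514 |
| 0.98 | 2.94 | 0.892 | >0.80 | 0.690 |
| 1.09 | 3.27 | 0.941 | 0.94 | 0.792 |
| 1.30 | 3.90 | 0.985 | >0.98 | 0.922 |

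The plan's figures reproduce at one-sided 0.05 without adjustment. The last column is the first Holm step, 0.05/5 = 0.01. Power of 0.80 at that level needs d = 1.10, above every d possible at 15%.

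**2. Bound the three unstated effect sizes.** Power of exactly 0.80 at one-sided 0.05 needs d = 0.846. The >0.80 claim therefore puts these three regions between 0.846 and 0.98 at 15%. At 20% the lower bound is 0.846 × 20/15 = 1.128, giving 1.128 to 1.30.

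**3. Power if Holm covers the five tests.** Full step-down Holm, one-sided, simulated with 100,000 trials. Values separated by semicolons follow the order of the d values.

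| Difference | d (amygdala; others) | r = 0.5 | r = 0.9 |
|---|---|---|---|
| 15% | 0.82; 0.846 × 3; 0.98 | 0.647; 0.667; 0.763 | 0.635; 0.645; 0.717 |
| 15% | evenly spaced, 0.82 to 0.98 | 0.662 to 0.775 | 0.658 to 0.729 |
| 15% | 0.82; 0.98 × 4 | 0.684; 0.791 | 0.698; 0.753 |
| 20% | 1.09; 1.128 × 3; 1.30 | 0.901 to 0.959 | 0.879 to 0.931 |
| 20% | 1.09; 1.30 × 4 | 0.923 to 0.969 | 0.920 to 0.948 |

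Even in the most favourable 15% case (four regions at d = 0.98), those four reach 0.80 only when r is about 0.3 or less (0.803 at r = 0.3). The chance of at least one Holm-significant region at 15% is 0.74 to 0.93.

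**4. Familywise error if Holm does not cover them.** Independent tests: 1 − 0.95⁵ = 0.226. Simulated with correlation: 0.167 (r = 0.5), 0.137 (r = 0.7), 0.096 (r = 0.9).

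**5. Sidedness.** The analysis paragraph does not repeat the one-tailed choice. At two-sided 0.05, with no multiplicity correction at all, power at 15% is 0.666 (d = 0.82) to 0.815 (d = 0.98).

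**6. A single test on average V_T.** If the regional SDs are equal, the effect size is mean d / √((1 + 4r)/5). With evenly spaced d at 15%, mean d = 0.90:
- r = 0.5: 0.90/√0.60 = 1.16, power 0.961
- r = 0.7: 0.90/√0.76 = 1.03, power 0.918
- r = 0.9: 0.90/√0.92 = 0.94, power 0.866

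Over the full range of d from step 2, power is 0.844 to 0.973.

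**The case against.** - **The power statement is honest about its terms.** It is labelled per region, one-tailed, 0.05, and marginal power is a common planning figure. This stands: there is no arithmetic error. The open question is whether it describes the planned tests.
- **The main scenario survives.** At 20%, every region keeps power of about 0.88 or more under Holm, and the study calls itself a proof-of-concept pilot. This also stands, and the sample size is not in question. But the plan labels the hypothesis primary and makes the 15% claim itself.
- **The voxel analysis is FDR-corrected and meant to confirm the regional results.** A lone regional finding would face that companion analysis, which does not control the error of the five regional tests.
- **Other readings are possible.** The plan writes of a general linear model in the singular, so one multivariate test is conceivable; the regional power figures would not describe that test either. If Holm spans the association models as well, the family exceeds five, and adjusted power for Hypothesis 1 can only be equal or lower. Both readings are further reasons to define the family.
- **The correlation and three effect sizes are assumed.** This is true, so ranges are given. Above r = 0.9 the uncorrected familywise error keeps falling (about 0.08 at r = 0.95) but stays above 0.05.

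**Conclusion.** The concern holds and should be fixed. The stated power is correct only for unadjusted one-sided tests at 0.05, and the plan leaves open whether those are the tests to be run. With Holm across five regions, power at a 15% difference is about 0.63 to 0.70 for amygdala (stated 0.77) and 0.64 to 0.79 for the other four (stated >0.80). At 20% it is about 0.88 to 0.97 (stated 0.94 to >0.98). Without Holm, the one-sided familywise error is about 0.10 to 0.17. These sizes rest on one-sided tests, a family of exactly five, equal correlations of 0.5 to 0.9, and effect sizes within the bounds the plan implies. The design is not undermined: the consequence falls on the 15% claim and on the rule for declaring Hypothesis 1 supported.

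**What to change.** In the Statistical Analysis Plan, state that Hypothesis 1 is tested by one general linear model per VOI (five tests), one-sided for higher V_T in smokers as in the power analysis, with Holm-Bonferroni across the five VOIs at a familywise 0.05. Say what counts as support for the hypothesis, and whether the association models form a separate family. Replace the regional power figures with Holm-adjusted ones and give the inter-VOI correlation they assume. That correlation can be estimated from the pooled baseline data (n = 21) already used, though imprecisely, so a range is advisable.

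An acceptable alternative is one prespecified primary test, such as the group effect on V_T averaged over the five VOIs, with Holm-adjusted regional follow-up.

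Either change costs only wording and restated figures, with no added participants or procedures. Keeping five tests makes the stated power at 15% less favourable; the single test gives up a primary claim about any particular region.

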All potential subjects will be screened by telephone using a standardized initial questionnaire, which includes demography, alcohol and drug use patterns and associated problems, and a brief personal medical and mental health status. This telephone screening addresses the major inclusion/exclusion criteria for the study and quickly rules out respondents who disqualify. We anticipate a highly adequate recruitment flow of subjects. In earlier studies, we completed a total of approximately 600 phone call inquiries and telephone screens annually. Based on our recent experience, we estimate we will consent and assess about 4 persons for each subject who completes study all procedures (i.e., approximately 72 participants will be consented in order to obtain 18 study completers). This is necessary to have a sufficient pool of subjects who meet inclusion/exclusion criteria and who can be matched to historical controls by sex, race/ethnicity, and age.

Subjects who appear eligible based on the telephone interview are informed of the general nature of the study, including study duration and commitment, introductory information about the medication, the nature of the measurement procedures, and compensation amount and arrangements. Interested volunteers are then invited for an in-person interview at the BPRU facilities on the Bayview Campus.

Screening.

Subjects who appear eligible and provide written informed consent will complete an in-person screening visit that includes a standard battery of instruments, a medical history, physical examination, vital signs, and standard blood chemistry and hematology laboratory tests. Prior to any research participation, subjects provide written informed consent using the Institutional Review Board (IRB) approved form; consent is obtained by IRB-approved members of the research team. Upon enrollment, subjects are assigned a unique study identifier (ID). Only subject IDs will be used to code all data forms.

Multiple assessment instruments will be done to determine who should be included and who excluded, and to provide measures that may be included as covariates in analyses. The Mini-International Neuropsychiatric Interview (MINI, v.7)⁽³⁶⁾ for DSM-5 will be used to assess TUD,

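### The Hypothesis 1 model contains group alone, so imbalance in age, sex or race left after matching to historical controls stays in the primary contrast, and covariate use is left open

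*Combined protocol and SAP*

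**What the plan says.** Section 7, Statistical Analysis Plan, sets out the Hypothesis 1 analysis as a general linear model in which V_T, transformed if necessary, "will be the dependent variable with group (smokers and controls) as the independent variable". No other term is named. For SPM it adds: "The same models used in VOI-based analyses will be applied to the voxel-based analyses". On confounding it says "Our intention is to frequency match groups as closely as possible for age, race, and sex", and it describes these variables as potential confounds. Baseline characteristics, including age, race and sex, are to be summarised and compared by group. No consequence for the model is attached to that comparison.

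Matching on age, sex and race is also stated in the Abstract, in Human Subjects Involvement, in the Controls paragraph of section 5, and under Sample size and Power Analysis. Human Subjects Involvement plans about 72 consents for 18 completers, partly so that matches can be found. Section 5 gives both groups the 21-50 age range and says the exclusion criteria were the same.

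Covariates are mentioned once, in section 4 under Screening, where assessments are made partly "to provide measures that may be included as covariates in analyses". No covariate, model or trigger is named.

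On sidedness, the power calculation uses an alpha "of 0.05 (one tailed test), we examined our power to detect a 20% difference between groups", and Hypothesis 1 is directional. The analysis sentence opens "To determine if smokers differ from controls in" and states no sidedness.

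**The concern.** Hypothesis 1 serves a primary objective, and its control arm comes from earlier protocols. Matching as closely as possible at 18 per group will usually leave some difference in age, sex or race. If V_T varies with any of these, the difference enters the group contrast in each VOI and in the SPM map. It can work for or against the hypothesis, and a model with group as its only term cannot take it out.

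The second issue is pre-specification. Because covariates are permitted but not named, an analyst could fit both the unadjusted and the adjusted model and choose between them after seeing V_T. With 36 people and a primary hypothesis, that choice should be made beforehand.

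**Working it through.** **1. The plan's own power.** Inputs from Sample size and Power Analysis: 18 v 18, one-sided 0.05, d = 1.09 to 1.3 for a 20% difference and 0.82 to 0.98 for 15%. A two-sample t-test has df = 34 and noncentrality d × sqrt(18/2) = 3d.

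| d | 3d | power | plan states |
|---|---|---|---|
| 0.82 | 2.46 | 0.778 | 0.77 |
| 0.98 | 2.94 | 0.892 | >0.80 |
| 1.09 | 3.27 | 0.941 | 0.94 |
| 1.30 | 3.90 | 0.985 | >0.98 |

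The stated figures reproduce. They are right for an unadjusted one-sided test.

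**2. Type I error of the group-only test when imbalance remains.** Neither r nor the imbalance is in the documents, so both are assumed. In units of the within-group SD of V_T, let V_T = d × group + r × x + e. Here x is a covariate standardised within group and held fixed, var(e) = 1 − r², and the group means of x differ by *imb*. The group-only t statistic is then Z / sqrt(W/34), where

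- Z is normal with mean 3(d + r × imb)/sqrt(1 − r²) and variance 1;
- W is noncentral chi-square with 34 df and noncentrality 34r²/(1 − r²).

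Example, d = 0, r = 0.3, imb = 0.25: the shift is 0.075 SD, the mean of Z is 0.225/0.954 = 0.236, and the noncentrality of W is 3.36. Numerical integration gives 0.068, or 0.026 if the imbalance runs the other way.

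One-sided 0.05, per VOI (imbalance favouring / opposing the hypothesis):

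| r | exact balance | 0.25 SD | 0.5 SD |
|---|---|---|---|
| 0 | 0.050 | 0.050 | 0.050 |
| 0.1 | 0.049 | 0.057 / 0.042 | 0.066 / 0.036 |
| 0.2 | 0.047 | 0.063 / 0.034 | 0.084 / 0.024 |
| 0.3 | 0.043 | 0.068 / 0.026 | 0.104 / 0.015 |
| 0.4 | 0.037 | 0.071 / 0.018 | 0.125 / 0.008 |

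A model that includes the covariate has rate 0.050 throughout. If Hypothesis 1 is tested two-sided, the group-only rates at r = 0.3 are 0.040 at balance, 0.046 at 0.25 SD and 0.062 at 0.5 SD.

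Scale: if ages were uniform over 21-50, their SD would be 29/sqrt(12) = 8.4 years. Then 0.25 SD is about 2.1 years of mean age and 0.5 SD about 4.2. For sex, 9 v 11 women of 18 is 0.225 SD and 9 v 13 is 0.468 SD.

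**3. Power on the same fixed-covariate model, r = 0.3.**

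| d | group-only, balance | group-only, 0.25 SD by direction | adjusted, balance | adjusted, 0.25 SD |
|---|---|---|---|---|
| 0.82 | 0.788 | 0.849 / 0.716 | 0.810 | 0.804 |
| 1.09 | 0.949 | 0.969 / 0.919 | 0.956 | 0.953 |

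**4. Cost of adjusting.** Age, sex and two-level race take 3 df, leaving 31. If they explain nothing and matching is close, power goes from 0.778 to 0.777 (d = 0.82) and from 0.941 to 0.940 (d = 1.09). With k mutually uncorrelated covariates each imbalanced by *imb*, the standard error is multiplied by sqrt(1 + k × imb² × 9/34). For k = 3 and imb = 0.5 this is sqrt(1.1985) = 1.095. If the covariates still explain nothing, power is about 0.71 at d = 0.82 and 0.90 at d = 1.09.

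**The case against.** The strongest reply is that confounding is handled by design. Matching is promised in several sections, recruitment is sized partly to allow it, and both groups share an age range and exclusion criteria. A simple contrast after matching is a recognised choice in a proof-of-concept pilot of 36. This stands as far as it goes: the plan makes no error of fact or arithmetic here, and close matching keeps any bias small. It does not deal with what matching leaves behind.

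A second reply is that the harm is assumed. That is also fair. At r = 0 there is no effect, at r = 0.1 it is slight, and under a two-sided test a 0.25 SD imbalance at r = 0.3 gives 0.046, below nominal. Marked inflation needs a one-sided test, imbalance in the unfavourable direction, a real correlation, and imbalance near 0.5 SD despite matching.

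Three stronger readings are tempting, and the documents do not support them.

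- A reader might infer that adjustment is ruled out. The Screening text permits covariates and a general linear model can hold them. The gap is the missing rule.
- A reader might treat the absence of a numerical matching tolerance as a defect in itself. Frequency matching is a firm commitment, and adjustment for the same variables deals with the remainder without a threshold.
- A reader might see a contradiction where the Protocol Overview lists age, sex and BMI. That list is introduced as examples and does not exclude race.

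**Conclusion.** The concern holds as a point about model choice and pre-specification. The primary contrast, in VOI and SPM form, has no protection in the model against residual imbalance in the three variables the plan itself names as potential confounds, and covariate use is left to later choice.

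The size and direction of any bias cannot be known from the documents. Over the assumed range (r from 0 to 0.4, one-sided), per-VOI type I error runs from 0.018 to 0.071 at a 0.25 SD imbalance and from 0.008 to 0.125 at 0.5 SD. With exact balance the group-only test is, if anything, conservative. A reader might infer that the test is anti-conservative as planned or that the power statement is wrong; neither follows. The case for the change rests on its low cost and on settling the model in advance, and does not depend on a particular r.

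**What to change.** Before smokers' V_T is examined, amend the Statistical Analysis Plan as follows. The timing is tied to smokers because V_T from 21 earlier baseline scans has already been used for the power calculation.

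- The primary Hypothesis 1 model, for VOI and SPM, is V_T on group + age + sex + race.
- Race coding is fixed from the matched sample's composition, collapsing sparse levels, without reference to V_T.
- The group-only model is reported as a sensitivity analysis.
- No other covariate, including those allowed under Screening, enters the primary model.

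The cost is wording and 3 residual degrees of freedom (4 with a third race level, where power is 0.776 at d = 0.82 and 0.939 at d = 1.09 under close matching). The price is material only when matching has gone badly on all three variables and they turn out unrelated to V_T, as in step 4 of the working. Age, sex and race must be held for both groups in order to match, so nothing new is collected. Aligning the Protocol Overview's example list with age, sex and race is optional tidying.

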- Meet DSM-V criteria for moderate to severe tobacco use disorder (TUD).

Controls (non-smokers): We will access a historical database of research participants that completed intake assessments and ¹⁸F-ASEM PET scans under our other comparable research studies (e.g., NA_00091295; IRB00185590; PI: [name]). Specifically, we will select males and females from our database of healthy nonsmokers who meet the following inclusion criteria: a) males and females aged 21-50 years, b) no current or past history of tobacco smoking, b) confirmed negative breath CO at intake and pre-PET (≤ 4 ppm). Exclusion criteria were the same as described below for smokers in the current protocol. We will select controls who are best matched for age, sex and race distributions to smokers in this study.

Exclusion Criteria:

- Meets DSM-V for AUD or SUD Disorder (excluding TUD for smokers)
- Meets DSM-V Psychiatric Disorder; in or in need of treatment
- Use of illicit drugs within last 90 days; positive urine toxicology screen
- Clinically-significant abnormality on ECG
- Unstable hypertension (BP > 150/90)
- Serum creatinine and hepatic enzymes (AST, ALT) outside of normal limits
- History of seizures, seizure disorder or closed head trauma
- HIV positive
- Weight > 350 lbs
- < 5th grade reading level as determined via a Shipley score of less than 18
- Use of smoking cessation products in last 3 months or undergoing current quit attempt using another treatment
- If female: has a positive pregnancy test, is pregnant, lactating, or planning pregnancy
- Significant anatomical abnormalities on MRI of the brain (e.g., enlarged ventricles, brain lesions)
- Use of prescribed medications in last 3 months; over the counter drugs or herbal supplements which may be counter indicated as determined by study physician may also be excluded
- Presence or history of drug allergy, or allergic disease diagnosed and treated by a physician.
- Any serious medical condition in whom participation is contraindicated.
- Any condition which would preclude MRI (e.g., implanted metal, severe claustrophobia).
- Radiation exposure in the last year that when combined with the study protocol would exceed the annual limits.

To determine eligibility, the medical records will be reviewed by study physicians, and psychological assessments and full inclusion/exclusion criteria will be reviewed by [name].

6. Drugs/ Substances/ Devices

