Derivation of outcome variables. There is no appropriate, reliable reference region for ^{18}F -ASEM due to the widespread distribution of $\alpha 7$ nAChR in the human brain. BP_{ND} (non-displaceable binding potential which requires a measure of absolute non-specific binding) is not appropriate for quantification of this radioligand. Volumes of Interest (VOI) will be generated by spatially normalizing⁽⁵⁶⁾ a standard VOI template⁽⁵⁷⁾ to individual subjects on Spoiled Gradient Recalled (SPGR) sequenced MRI volumes. VOIs are: amygdala, ventral striatum, cingulate, hippocampus, and frontal cortex. $\alpha 7$ nAChR availability (V_T) will be obtained for each VOI by plasma reference graphical analysis (PRGA); we have previously demonstrated that PRGA showed more robust estimates of V_T than the two-compartment model, as measured with time dependency of estimates and the magnitude of inter-subject variability⁽⁵⁴⁾. V_T is a standard outcome for many receptor binding radiopharmaceuticals.

Sample size and Power Analysis: We propose a total sample size of 36, which includes 18 smokers accrued in the proposed study, plus an equal number ($n=18$) of healthy nonsmokers selected from a

pooled sample of our historical database, matching for basic demographic variables (age, sex, and race) of our smokers.

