Resting-state functional brain connectivity analysis: Resting-state data will undergo standard preprocessing step, including slice timing correction, realignment/motion correction, co-registration across runs and to the SPM EPI template⁽⁵⁹⁾, with smoothing, motion sensoring or “scrubbing”⁽⁶⁰⁾, physiological artifact correction⁽⁶¹⁾, and 36-parameter confound regression and spike regression⁽⁶²⁾. DTI and structural MRI data will undergo realignment, registration to an average template, and deterministic tractography will be conducted in order to determine laplacian harmonics for connectome harmonic analysis. Seed-based, region-of-interest-based⁽⁶³⁾, independent component-based⁽⁵⁹⁾, graph-theory/network-analysis-based⁽⁶⁴⁾, and connectome-harmonic-based metrics⁽⁶⁵⁾ of

connectivity within and among commonly identified resting-state networks^(66, 67)), including the default mode, salience, executive control, and fronto-parietal attention networks will be determined using standard software. These metrics will be compared between groups (smokers and matched controls) using a two-sample T-test.

8. Risks

- a. Medical risks, listing all procedures, their major and minor risks and expected frequency.

This study involves several separate procedures, each of which entails some risk of discomfort or side effects. These risks are discussed by procedure. Participants will receive a thorough description of all potential risks in the consent document.

Screening procedures: This study involves questions about dangerous or illegal behavior, psychiatric history, a medical history, and a physical exam. There is risk of a possible breach of confidentiality. There is also a small risk that participants will become upset during the screening interview. Participants' names will be recorded only on the screening, informed consent, and necessary medical and payment forms. Anonymous participant identification numbers will be used on all other forms and labeling of biological fluids and test results.

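### Resting-state connectivity: an open list of metrics goes to a two-sample t-test, with no multiplicity rule that clearly covers it and no group-level adjustment for head motion

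*Combined protocol and SAP*

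**What the plan says.** The resting-state paragraph of Section 7 names five ways of deriving metrics: seed, region of interest, independent component, graph/network and connectome harmonic. They describe "connectivity within and among commonly identified resting-state networks". Four networks are named, but as examples, so the list is open. The group analysis is one sentence: "These metrics will be compared between groups (smokers and matched controls) using a two-sample T-test". No primary metric, alpha, sidedness, covariate or number of tests is given.

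Two corrections appear in the preceding Statistical Analysis Plan paragraph. One is the threshold for the voxel-wise V_T maps: "FDR-corrected, and the minimal cluster size at 50 voxels". The other closes the paragraph, directly after the models relating V_T to withdrawal measures: "The Holm-Bonferroni method will be applied to correct for multiple comparisons". Its scope is not stated.

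Head motion is treated in preprocessing by realignment, scrubbing and "36-parameter confound regression and spike regression". It is not a matching variable. The Abstract says "Study participants and historical controls will be matched by race, sex, and age"; Section 5 says "We will select controls who are best matched for age, sex and race distributions to smokers in this study"; the sample size paragraph of Section 7 says "matching for basic demographic variables (age, sex, and race) of our smokers". The Protocol Overview in Section 4a gives age, sex and BMI as examples. None of these places mentions motion.

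**The concern.** There are two separate routes to a spurious finding.

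- **Multiplicity.** Many metrics are tested and the list is not fixed in advance. Some will differ between 18 smokers and 18 controls by chance, and nothing clearly says how that is controlled.
- **Motion.** Preprocessing removes motion-related signal scan by scan, but may leave some behind. If smokers and controls move by different amounts, the remainder becomes a difference in group means. A two-sample t-test has no term to separate it from a smoking effect.

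At stake is whether a connectivity difference reported between smokers and nonsmokers can be believed.

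**Working it through.** **1. Check of the formula on the plan's own figures.** The plan gives no power for connectivity. Its only group-comparison power is for V_T (Section 7, 18 per group, one-sided 0.05). With noncentrality d × √(18/2) = 3d and 34 df:

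| d | Plan | Recomputed |
|---|---|---|
| 1.09 | 0.94 | 0.941 |
| 1.3 | >0.98 | 0.985 |
| 0.82 | 0.77 | 0.778 |
| 0.98 | >0.80 | 0.892 |

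The figures reproduce, so the same formula is used below, two-sided.

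**2. Number of tests (assumed).** One test per family and named network gives 5 × 4 = 20. Adding the six pairs among four networks gives 5 × (4 + 6) = 50.

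**3. Chance of at least one false positive.** Assumptions: no true differences, uncorrected two-sided 0.05, and equal correlation ρ between metrics.

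- Independent: 1 − 0.95^m, so 1 − 0.95^20 = 0.642 and 1 − 0.95^50 = 0.923.
- Correlated: 1 − ∫ φ(u) [Φ((z − √ρ·u)/√(1 − ρ)) − Φ((−z − √ρ·u)/√(1 − ρ))]^m du, with z = 1.96.

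| Tests | ρ = 0.8 | ρ = 0.5 | Independent |
|---|---|---|---|
| 20 | 0.224 | 0.419 | 0.642 |
| 50 | 0.299 | 0.622 | 0.923 |

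Simulated t-tests with 18 per group (20,000 replicates) gave 0.237 and 0.428 for 20 tests, and 0.309 and 0.634 for 50. The metrics come from the same scans, so the correlated columns are the relevant ones.

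**4. Motion.** Let the groups differ by D SD in mean motion, and let a metric correlate r with motion after denoising. With no true effect, the metric then differs by d = D × r. Rejection rate of one two-sided t-test (noncentrality 3·D·r, 34 df):

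| D | r = 0.1 | r = 0.2 | r = 0.3 | r = 0.4 |
|---|---|---|---|---|
| 0.3 | 5.1% | 5.4% | 5.8% | 6.4% |
| 0.5 | 5.2% | 6.0% | 7.2% | 9.0% |
| 1.0 | 6.0% | 9.0% | 14.1% | 21.5% |

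Simulation (40,000 replicates) at r = 0.3 and 0.4 gave 7.4% and 9.1% for D = 0.5, and 14.3% and 21.8% for D = 1. A linear model with motion as covariate stayed at 4.9% to 5.2%. That simulation makes the metric a linear function of motion, which suits the model.

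**5. Power after the change.** The effect size d = 1.09 is borrowed from amygdala V_T, because the plan gives none for connectivity.

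- t-test: noncentrality 3 × 1.09 = 3.27, 34 df, power 0.888. At d = 0.8 it is 0.645 and at d = 0.5 it is 0.308.
- Group plus motion: noncentrality 3.27 × √(1 − R²), 33 df, where R² = D²/(D² + 4) is the share of group membership that motion explains. At D = 0, 0.5 and 1, R² is 0, 0.059 and 0.20, and power is 0.888, 0.868 and 0.810.
- Adding age, sex and one race indicator (30 df) gives 0.886, 0.866 and 0.808 at R² of 0, 0.06 and 0.20.
- FDR (Benjamini-Hochberg, simulated, 30 df, correlation 0.5, from one to half of the metrics truly different): average power is 0.50 to 0.76 for 20 tests and 0.38 to 0.76 for 50 at R² = 0. At R² = 0.20 it is 0.38 to 0.63 and 0.27 to 0.62.

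**The case against.** **The Holm sentence may be general.** It sits in Section 7 and has no stated scope, so a reader might go too far in inferring that the plan tests connectivity with no correction at all. The documents do not establish that. What stands is that the rule does not clearly reach these tests. Even if it does, Holm needs a defined family of tests, and the resting-state paragraph does not fix one.

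**Motion is treated thoroughly within subject.** A reader might infer that the plan ignores head motion. It does not: realignment, scrubbing, physiological correction and confound regression are all specified, so a weak residual correlation is quite plausible. Section 4b also places the smokers' MRI at the smoking-as-usual visit, so withdrawal restlessness is not an expected source of imbalance. Error rates near 5% are therefore as credible as the higher ones. What stands is that nothing at group level handles a difference if one exists.

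**Matching.** Planned matching on age, sex and race leaves only residual imbalance in those variables. Adjusting for them is optional.

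**Control scans.** The Protocol Overview and Retrospective Healthy Control Data paragraphs of Section 4a describe control data as PET, and Section 5 adds intake assessments. Resting-state and diffusion scans are described only for this study's participants (MRI Procedures). A reader might infer that the controls have no such scans and that the comparison is impossible. The text does not show that: the volume-of-interest step in Section 7 implies that controls have an anatomical MRI, and the control protocols, not supplied here, may settle the rest. This is a request for clarification.

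**Conclusion.** The point holds, as a minor one. The resting-state comparison has an open list of tests, no multiplicity rule that clearly covers it, and no group-level term for motion.

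If the tests were uncorrected at two-sided 0.05, the chance of some false positive would be 22% to 42% for 20 tests and 30% to 62% for 50, at correlations of 0.8 to 0.5. The 64% and 92% under independence are upper ends, not expectations. For motion, each test's error rate runs from about 5% (0.3 SD difference, residual correlation 0.1) through 7% to 9% (0.5 SD, 0.3 to 0.4). It reaches 14% to 22% only in the extreme case (1 SD, 0.3 to 0.4). Test counts, correlations, alpha, sidedness and motion values are all assumptions, and the documents favour no particular value.

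A reader might extend this to the trial's main conclusion. That is not supported: connectivity serves none of Hypotheses 1 to 4, and the V_T comparison has its own model.

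**What to change.** Before analysis:

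1. Label the comparison exploratory, fix the list of metrics and networks, and apply FDR at 0.05 across that list.
2. Replace the t-test with a linear model of group plus mean head motion, taken from the realignment already planned. Age, sex and race can be added if matching leaves imbalance.
3. As a clarification, state the source and acquisition of the control resting-state and diffusion scans.

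No new smoker scans are needed. The cost is power per metric. At d = 1.09, the motion term alone takes single-test power from 0.89 to between 0.81 and 0.89 for group differences in motion of up to 1 SD. FDR lowers it further, to between 0.27 and 0.76 across the cases shown. For smaller effects power is already low with the t-test (0.65 at d = 0.8 and 0.31 at d = 0.5), which is a further reason for the exploratory label.
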